### 5.4 **Definition of Dose-Limiting Toxicity (DLT)**

DLT will be defined as any of the following events that are possibly, probably or definitely attributable to protocol therapy. Dose limiting hematological and non-hematological toxicities are defined differently.

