#### 5.4.2 Hematological dose limiting toxicity

5.4.2.1 Hematological dose limiting toxicity is defined as:

- a) In patients evaluable for hematological toxicity (see [Section 6.1](#)),
  - Grade 4 thrombocytopenia or neutropenia, not due to malignant infiltration
  - Grade 3 thrombocytopenia that persists for  $\geq 7$  days
  - Grade 3 thrombocytopenia requiring a platelet transfusion on two separate days within a 7-day period
  - Grade 3 thrombocytopenia with clinically significant bleeding
  - Neutropenia or thrombocytopenia that causes a delay of  $> 14$  days between treatment cycles" (e.g. platelets <100K or ANC<1000).

5.4.2.2 Note: Grade 3 or 4 febrile neutropenia will not be considered a dose-limiting toxicity.

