## 6.0 DOSE MODIFICATIONS FOR ADVERSE EVENTS

**The Study Chair must be notified of any dosage modification or use of myeloid growth factor.**

### 6.1 Dose Modifications for Hematological Toxicity

- 6.1.1 If a patient experiences hematological dose-limiting toxicity as defined in [Section 5.4.2.1](#), the treatment will be held. Counts should be checked every 3-4 days for thrombocytopenia and every other day for neutropenia during this time. If the toxicity resolves to meet eligibility parameters within 14 days of drug discontinuation, the patient may resume treatment at a reduced dose (see [Appendix IV-A](#) for capsule formulation dosing nomogram and [Appendix IV-B](#) for preparation of liquid formulation). Doses reduced for toxicity will not be re-escalated, even if there is minimal or no toxicity with the reduced dose.
- 6.1.2 If toxicity does not resolve to meet eligibility parameters within 14 days of drug discontinuation, the patient must be removed from protocol therapy.
- 6.1.3 If hematological dose-limiting toxicity recurs in a patient who has resumed treatment at the reduced dose, the patient must be removed from protocol therapy.

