## 8.0 EVALUATIONS/MATERIAL AND DATA TO BE ACCESSIONED

## 8.1 Required Clinical, Laboratory and Disease Evaluation

All clinical and laboratory studies to determine eligibility must be performed within 7 days prior to enrollment unless otherwise indicated. Laboratory values used to assess eligibility (see [Section 4.0](#)) must be no older than seven (7) days at the start of therapy. Laboratory tests need **not** be repeated if therapy starts **within** seven (7) days of obtaining labs to assess eligibility. If a post-enrollment lab value is outside the limits of eligibility, or laboratory values are older than 7 days, then the following laboratory evaluations must be re-checked within 48 hours prior to initiating therapy: CBC with differential, bilirubin, ALT (SGPT) and serum creatinine. If the recheck is outside the limits of eligibility, the patient may not receive protocol therapy and will be considered off protocol therapy. Imaging studies, bone marrow aspirate and/or biopsy, must be obtained within 14 days prior to start of protocol therapy (repeat the tumor imaging if necessary).

STUDIES TO BE OBTAINED	Pre-Study	During Cycle 1	Prior to Subsequent Cycles ^
History	X	Weekly	X
Physical Exam with vital signs	X	Weekly	X
Neurologic Exam	X		
Height, weight, BSA	X		X
Performance Status	X		
Pregnancy Test 	X		
CBC, differential, platelets	X	Twice Weekly (every 3 to 4 days) 	Weekly 
Urinalysis	X		
Electrolytes including Ca ++ , PO 4 , Mg ++	X	Weekly	X
Creatinine, ALT, bilirubin	X	Weekly	X
Albumin	X		X
Tumor Disease Evaluation 4-A, 4-B, 4-C	X		Every other cycle x 3 then q 3 cycles 
Bone Marrow Aspirate and/or biopsy 	X 		
Medication Diary 		Weekly	X
Pharmacokinetics (optional) 	X	X	
Circulating Tumor DNA (ctDNA-optional) 			Cycle 5, Day 1 and (for patients receiving ≥ 5 cycles only) at end of Protocol Therapy OR disease progression

^ Studies may be obtained within 72 hours prior to the start of the subsequent cycle.

 Women of childbearing potential require a negative pregnancy test prior to starting treatment; sexually active patients must use an acceptable method of birth control. Abstinence is an acceptable method of birth control.

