 If patients have Grade 4 neutropenia then CBCs should be checked at least every other day until recovery to Grade 3 or until meeting the criteria for dose limiting toxicity.

 If patients develop Grade 4 thrombocytopenia then CBCs should be checked every 3 to 4 days until recovery, per [Section 6.1](#).

 Tumor Disease Evaluation should be obtained on the next consecutive cycle after initial documentation of either a PR or CR. Subsequent scans may restart 2 cycles after the confirmatory scan. If the institutional investigator determines that the patient has progressed based on clinical or laboratory

evidence, he/she may opt not to confirm this finding radiographically.

- 4-A Neurological exam also required for CNS patients.
- 4-B Non- Hodgkin Lymphoma/ Histiocytosis patients are required to have PET scans within 2 weeks prior to start of therapy and should also be followed with PET scans if positive at diagnosis. Refer to [Section 12.8](#)
- 4-C Patients with neuroblastoma must have both CT/MRI and MIBG scintigraphy prior to enrollment if the patient was enrolled with or has a history of having MIBG avid tumor. Otherwise the patient must have both CT/MRI and bone scan prior to enrollment. For patients with neuroblastoma and measurable disease by CT or MRI, lesions should be measured and followed using the same modality (CT or MRI) in addition to MIBG or bone scan. For patients with neuroblastoma and evaluable disease by MIBG scintigraphy or bone scan, use the same modality (MIBG scintigraphy or bone scan) to image and follow patients; CT/MRI are not required but may be performed as clinically indicated. Refer to [Section 12.5.4](#) and [Section 12.9](#).
- 5 Bone marrow aspirate and/or biopsy only required in patients suspected of having bone marrow metastasis on the basis of history, symptoms, laboratory evaluation or other clinical data. Should only be performed on patients with known bone marrow involvement at baseline.
- 6 Bone marrow aspirate and/or biopsy should be performed only when complete response or partial response is identified in target disease or when progression in bone marrow is suspected.
- 7 Medication diary (see [Appendix III](#)) should be reviewed weekly during cycle 1, after completion of each treatment cycle, and uploaded into RAVE.
- 8 See [Section 8.3](#) for details of PK studies.

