a.	History/Physical Exam (including VS)
b.	Ht/Wt/BSA
c.	CBC/differential/platelets If patients develop Grade 4 neutropenia then CBCs should be checked every 3 to 4 days until recovery to Grade 3
d.	Electrolytes including Ca++, PO4, Mg++
e.	Creatinine, ALT, bilirubin
f.	Albumin
g.	Tumor Disease Evaluation – Every other cycle x 3 then q 3 cycles. Tumor Disease Evaluation should be obtained on the next consecutive cycle after initial documentation of either a PR or CR. Subsequent scans may restart 2 cycles after the confirmatory scan. If the institutional investigator determines that the patient has progressed based on clinical or laboratory evidence, he/she may opt not to confirm this finding radiographically
h.	Bone Marrow Aspirate and/or biopsy- Every other cycle x 3 then q 3 cycles. Only required in patients suspected of having bone marrow metastasis on the basis of history, symptoms, laboratory evaluation or other clinical data. Should only be performed on patients with known bone marrow involvement at baseline. Bone marrow aspirate and/or biopsy should be performed only when complete response or partial response is identified in target disease or when progression in bone marrow is suspected.
i.	Medication Diary- (see Appendix III-A and Appendix III-B ) should be reviewed after completion of each treatment cycle and uploaded into RAVE. The medication diary should be collected weekly.
j.	Circulating Tumor DNA (ctDNA-optional)- With consent, two samples will be collected on this protocol (Cycle 5 Day 1; and for patients receiving $\geq 5$ cycles, at progression or end of protocol therapy) see Section 8.4 for details of the ctDNA studies.
k.	Pharmacokinetics (optional)-see Section 8.3 for details of PK studies.

**This listing only includes evaluations necessary to answer the primary and secondary aims. OBTAIN OTHER STUDIES AS REQUIRED FOR GOOD CLINICAL CARE.**

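### The delivery map for cycles after the first sets blood counts every 3 to 4 days for Grade 4 neutropenia, where Section 8.1 requires at least every other day

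*Combined protocol and SAP*

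**What the plan says.** Five places set the frequency of blood counts for a patient with Grade 4 cytopenia.

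- **Section 8.1, evaluation table and footnote 2.** The CBC row is twice weekly in Cycle 1 and weekly in later cycles. Both entries carry footnotes 2 and 3. Footnote 2 says that in Grade 4 neutropenia "CBCs should be checked at least every other day until recovery to Grade 3 or until meeting the criteria for dose limiting toxicity".
- **Section 8.1, footnote 3.** "If patients develop Grade 4 thrombocytopenia then CBCs should be checked every 3 to 4 days until recovery".
- **Section 6.1.1**, during a hold for hematological DLT: "Counts should be checked every 3-4 days for thrombocytopenia and every other day for neutropenia during this time".
- **Appendix VI, Cycle 1 map, item b.** This repeats the footnote 2 rule for neutropenia.
- **Appendix VI, all subsequent cycles, item c.** "If patients develop Grade 4 neutropenia then CBCs should be checked every 3 to 4 days until recovery to Grade 3".

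The later-cycle map is to be copied for each cycle. It refers to Section 8.1 for timing only on items marked with an asterisk (g, h, j and k). Item c has no asterisk. The page also refers to Section 6.0 for dose modifications.

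**The concern.** Item c gives Grade 4 neutropenia an interval that the main text gives only to thrombocytopenia and to routine Cycle 1 counts. Treatment may run to 26 cycles (Section 5.1), so this page covers up to 26 − 1 = 25 of them. A site that follows its own worksheet literally would check counts less often than Section 8.1 requires, and nothing in item c would alert it.

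At stake are the monitoring of children with very low neutrophil counts and site compliance with the protocol. There may also be a small effect on the recorded duration of Grade 4 events, since Section 13.4.3 takes an event's duration as the time spent at its highest grade. The event is plausible at this dose: Section 2.5.1 reports Grade 3/4 neutropenia in 2 of 10 children treated at 100 mg/m² BID, without separating the grades or naming the cycle.

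**Working it through.** There is no sample size, power or error rate to reproduce here. The check compares texts and adds simple arithmetic on the intervals.

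**1. Does footnote 2 govern later cycles?** Yes. Its marker is on the later-cycle CBC entry as well as the Cycle 1 entry, and its text has no cycle limit.

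**2. The rules side by side**

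| Source | Grade 4 neutropenia | Thrombocytopenia |
|---|---|---|
| 8.1 footnotes 2 and 3 (all cycles) | at least every 2 days | every 3–4 days (Grade 4) |
| 6.1.1 (hold for hematological DLT) | every 2 days | every 3–4 days |
| Appendix VI, Cycle 1 map | at least every 2 days | no rule |
| Appendix VI, later-cycle map, item c | **every 3–4 days** | no rule |

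Item c is the only entry that differs for neutropenia. Its interval matches the thrombocytopenia rule, which may point to a copying slip, but the documents do not state a cause.

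**3. Which patients depend on footnote 2 alone?** Section 6.1.1 begins "If a patient experiences hematological dose-limiting toxicity as defined in" Section 5.4.2.1, so it applies only to a hematological DLT. That definition covers "Grade 4 thrombocytopenia or neutropenia, not due to malignant infiltration" in patients evaluable for hematological toxicity, and Section 5.4 limits DLTs to "any of the following events that are possibly, probably or definitely attributable to protocol therapy". When those conditions are met, the map's reference to Section 6.0 leads to the correct interval, although item c makes no exception and still conflicts on its face. Section 6.1.1 is not triggered in these cases:

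- patients with known marrow disease, who are not evaluable for hematologic toxicity (Section 4.1.6.1 b);
- neutropenia due to malignant infiltration (Section 5.4.2.1), which overlaps with the first group;
- events not at least possibly attributable to therapy (Section 5.4).

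Section 5.4.2.2 also says that febrile neutropenia is not a DLT. That could widen the group, but a Grade 4 neutrophil count remains a DLT under 5.4.2.1 when it is attributable and the patient is evaluable.

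In these cases footnote 2 is the only rule that contradicts item c.

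**4. Size of the difference.** Inputs: at most 2 days between counts (footnote 2), 3 to 4 days (item c), 7 days (routine later-cycle count).

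- Extra days between counts: 3 − 2 = 1 to 4 − 2 = 2.
- Ratio of intervals: 3/2 = 1.5 to 4/2 = 2.0.
- Rate relative to the required minimum: 2/4 = 50% to 2/3 = 67%.
- Increase over weekly counts: at least 7/2 = 3.5-fold under footnote 2, against 7/4 = 1.75-fold to 7/3 = 2.33-fold under item c.
- Illustration for an assumed 14-day episode: at least 14/2 = 7 counts under footnote 2. Under item c, 14/4 = 3.5 gives 3 complete intervals and 14/3 = 4.67 gives 4, so 3 to 4 counts.

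The documents give no rate or duration of Grade 4 neutropenia after Cycle 1 and no share of patients with marrow disease. No number of affected patients can be derived.

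**The case against.** The strongest reply is that this is an editorial slip with little consequence.

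- Attributable Grade 4 neutropenia in an evaluable patient is a DLT at onset. Footnote 2 then ends by its own terms, and Section 6.1.1 requires a hold with counts every other day.
- The remaining group is probably small. Larotrectinib is the only anticancer agent allowed during treatment (Section 7.1), decreased neutrophil count is a listed possible effect (Section 9.1.9), and possible attribution is enough for a DLT.
- Patients with marrow disease must have an ANC of at least 1000/mm³ at entry (Section 4.1.6.1), and laboratory criteria must be met again before each cycle (Section 5.2).
- For non-DLT neutropenia, Section 6.1 attaches no hold or dose reduction to the extra counts.
- Toxicity tables use the worst grade per patient (Section 11.4), and Grade 4 has already been recorded when item c applies.
- The page is not a ceiling, because it also asks for whatever else good clinical care requires.

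Most of this stands as a limit on the consequences: few patients are likely to be exposed, and the worst-grade tables do not change. It does not remove the contradiction. The safeguards at entry and at cycle start do not set how often counts are taken during a Grade 4 episode within a cycle. The good-care note leaves to judgement what Section 8.1 makes a requirement. Nor does the text suggest a deliberate relaxation: footnote 2 is still attached to the later-cycle entry, 6.1.1 has no cycle limit, and no rationale is given.

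**Conclusion.** The concern holds. Item c of the later-cycle map contradicts Section 8.1 footnote 2 and, for DLT cases read literally, Section 6.1.1. It lengthens the gap between counts in Grade 4 neutropenia by 1 to 2 days, to 50% to 67% of the minimum rate that Section 8.1 sets. The practical effect falls mainly on Grade 4 neutropenia that is not a DLT. That view assumes that sites follow the map's reference to Section 6.0 when a DLT occurs.

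This is an inconsistency in an operational safety rule, not a flaw in the design. The response endpoint, the decision rule, the sample size and the error rates are unaffected. It should be corrected because the page is a working document used in every cycle after the first.

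**What to change.** Replace the Grade 4 neutropenia sentence in item c with the footnote 2 rule: for a patient with Grade 4 neutropenia, "CBCs should be checked at least every other day until recovery to Grade 3 or until meeting the criteria for dose limiting toxicity", and thereafter as Section 6.1 directs. Adding the same pointer to Section 6.1 in item b of the Cycle 1 map would keep the two pages matched.

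Optionally, add the footnote 3 thrombocytopenia interval to both maps, since neither has it now.

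The required change is one line in Appendix VI. It restores a rule already in the protocol and needs no change to the design, data collection or analysis.

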**Comments**

(Include any held doses, or dose modifications)

Treatment Details: Subsequent Cycles

Following completion of this cycle, the next cycle starts on Day 29 or when the criteria in [Section 5.2](#) are met (whichever occurs later).

**APPENDIX VII: TARGET HISTOLOGIES FOR APEC1621A EXPANSION COHORTS**

**Target tumor types considered for biomarker-positive expansion cohorts in the event of agent activity in a specific tumor type.**

Tumor type
1. Ependymoma
2. Ewing Sarcoma/Peripheral PNET
3. Hepatoblastoma
4. Glioma, high grade
5. Glioma, low grade
6. Langerhans Cell Histiocytosis
7. Malignant Germ Cell Tumor
8. Medulloblastoma
9. Neuroblastoma
10. Non-Hodgkin Lymphoma
11. Non-RMS Soft Tissue Sarcoma
12. Osteosarcoma
13. Rhabdoid Malignancy
14. Rhabdomyosarcoma
15. Wilms Tumor
16. Other Histology (based on COG/NCI-CTEP approval)

**APPENDIX VIII: EXAMPLES OF ACTIONABLE MUTATIONS FOR SUB-PROTOCOL  
APEC1621A**

INCLUSION	VARIANTS			
Fusions				
Gene Name	Variant ID	Variant Type	LOE	Variant Description
NTRK1	NTRK1-DYNC2H1.N17D85	Fusion	3	NTRK1 Gene Fusion
NTRK1	TPM3-NTRK1.T7N13	Fusion	3	NTRK1 Gene Fusion
NTRK1	LMNA-NTRK1.L3N11	Fusion	3	NTRK1 Gene Fusion
NTRK1	TPM3-NTRK1.T8N10	Fusion	3	NTRK1 Gene Fusion
NTRK1	TPM3-NTRK1.T7N10.COSF1329	Fusion	3	NTRK1 Gene Fusion
NTRK1	TPR-NTRK1.T21N10.COSF1326	Fusion	2	NTRK1 Gene Fusion
NTRK1	TPR-NTRK1.T6N12.COSF1324	Fusion	2	NTRK1 Gene Fusion
NTRK1	MPRIP-NTRK1.M14N12	Fusion	3	NTRK1 Gene Fusion
NTRK1	MPRIP-NTRK1.M18N12	Fusion	3	NTRK1 Gene Fusion
NTRK1	MPRIP-NTRK1.M21N12	Fusion	3	NTRK1 Gene Fusion
NTRK1	SQSTM1-NTRK1.S5N10	Fusion	3	NTRK1 Gene Fusion
NTRK1	SSBP2-NTRK1.S12N12	Fusion	3	NTRK1 Gene Fusion
NTRK1	TFG-NTRK1.T6N10	Fusion	3	NTRK1 Gene Fusion
NTRK1	BCAN-NTRK1.B13N11	Fusion	3	NTRK1 Gene Fusion
NTRK1	LMNA-NTRK1.L2N11	Fusion	3	NTRK1 Gene Fusion
NTRK1	NFASC-NTRK1.N20N10	Fusion	3	NTRK1 Gene Fusion
NTRK1	RNF213-NTRK1.R15N12	Fusion	3	NTRK1 Gene Fusion
NTRK1	IRF2BP2-NTRK1.I1N10.1	Fusion	3	NTRK1 Gene Fusion
NTRK1	TPR-NTRK1.T6N12.1	Fusion	3	NTRK1 Gene Fusion
NTRK1	CD74-NTRK1.C7N10	Fusion	3	NTRK1 Gene Fusion
NTRK1	SQSTM1-NTRK1.S2N10	Fusion	3	NTRK1 Gene Fusion
NTRK1	TP53-NTRK1.T10N9	Fusion	3	NTRK1 Gene Fusion
NTRK1	LMNA-NTRK1.L10N12	Fusion	3	NTRK1 Gene Fusion
NTRK1	RABGAP1L-NTRK1.R14N16	Fusion	3	NTRK1 Gene Fusion
NTRK1	CHTOP-NTRK1.C5N11	Fusion	3	NTRK1 Gene Fusion
NTRK1	TP53-NTRK1.T8N9	Fusion	3	NTRK1 Gene Fusion
NTRK1	TP53-NTRK1.T9N9	Fusion	3	NTRK1 Gene Fusion
NTRK1	PPL-NTRK1.P12N13	Fusion	3	NTRK1 Gene Fusion
NTRK1	TFG-NTRK1.T6N14	Fusion	3	NTRK1 Gene Fusion
NTRK1	TP53-NTRK1.T11N9	Fusion	3	NTRK1 Gene Fusion
NTRK1	ARHGEF2-NTRK1.A21N10	Fusion	3	NTRK1 Gene Fusion
NTRK1	EPHB2-NTRK1.E3N9	Fusion	3	NTRK1 Gene Fusion
NTRK1	CHTOP-NTRK1.C5N10	Fusion	3	NTRK1 Gene Fusion

NTRK1	LMNA-NTRK1.L10N11	Fusion	3	NTRK1 Gene Fusion
NTRK1	TPR-NTRK1.T21N9	Fusion	3	NTRK1 Gene Fusion
NTRK1	EPS15-NTRK1.E21N9	Fusion	3	NTRK1 Gene Fusion
NTRK1	PPL-NTRK1.P22N11	Fusion	3	NTRK1 Gene Fusion
NTRK1	PPL-NTRK1.P22N10	Fusion	3	NTRK1 Gene Fusion
NTRK1	EPS15-NTRK1.E21N9.1	Fusion	3	NTRK1 Gene Fusion
NTRK1	LMNA-NTRK1.L11N11	Fusion	3	NTRK1 Gene Fusion
NTRK1	TPM3-NTRK1.T7N12	Fusion	3	NTRK1 Gene Fusion
NTRK1	LMNA-NTRK1.L5N10	Fusion	3	NTRK1 Gene Fusion
NTRK1	LMNA-NTRK1.L6N12	Fusion	3	NTRK1 Gene Fusion
NTRK1	MRPL24-NTRK1.M1N9.1	Fusion	3	NTRK1 Gene Fusion
NTRK1	NTRK1-NTRK1.N6N8	Fusion	3	NTRK1 Gene Fusion
NTRK1	MRPL24-NTRK1.M1N9	Fusion	3	NTRK1 Gene Fusion
NTRK1	TPM3-NTRK1.T7N7.ins	Fusion	3	NTRK1 Gene Fusion
NTRK1	CEL-NTRK1.C7N7.2	Fusion	3	NTRK1 Gene Fusion
NTRK1	TPR-NTRK1.T16int9N10	Fusion	3	NTRK1 Gene Fusion
NTRK2	NACC2-NTRK2.N4N13.COSF1448	Fusion	3	NTRK2 Gene Fusion
NTRK2	QKI-NTRK2.Q6N16.COSF1446	Fusion	3	NTRK2 Gene Fusion
NTRK2	AFAP1-NTRK2.A14N12	Fusion	3	NTRK2 Gene Fusion
NTRK2	AGBL4-NTRK2.A6N16	Fusion	3	NTRK2 Gene Fusion
NTRK2	SQSTM1-NTRK2.S5N17	Fusion	3	NTRK2 Gene Fusion
NTRK2	TRIM24-NTRK2.T12N15	Fusion	3	NTRK2 Gene Fusion
NTRK2	VCL-NTRK2.V16N12	Fusion	3	NTRK2 Gene Fusion
NTRK2	DAB2IP-NTRK2.D1N17	Fusion	3	NTRK2 Gene Fusion
NTRK2	TRIM24-NTRK2.T12N16	Fusion	3	NTRK2 Gene Fusion
NTRK2	NAV1-NTRK2.N15N11	Fusion	3	NTRK2 Gene Fusion
NTRK2	SLMAP-NTRK2.S14N16	Fusion	3	NTRK2 Gene Fusion
NTRK3	NTRK3-HOMER1.N17H2	Fusion	3	NTRK3 Gene Fusions
NTRK3	ETV6-NTRK3.E4N15.COSF823.2	Fusion	2	NTRK3 Gene Fusions
NTRK3	ETV6-NTRK3.E5N15.COSF571.1	Fusion	2	NTRK3 Gene Fusions
NTRK3	BTBD1-NTRK3.B4N14	Fusion	3	NTRK3 Gene Fusions
NTRK3	COX5A-NTRK3.C1N15	Fusion	3	NTRK3 Gene Fusions
NTRK3	ETV6-NTRK3.E4N14.1	Fusion	2	NTRK3 Gene Fusions
NTRK3	ETV6-NTRK3.E5N14	Fusion	2	NTRK3 Gene Fusions
NTRK3	FAT1-NTRK3.F2N7	Fusion	3	NTRK3 Gene Fusions
NTRK3	EML4-NTRK3.E2N14	Fusion	3	NTRK3 Gene Fusions
NTRK3	AKAP13-NTRK3.A14N14	Fusion	3	NTRK3 Gene Fusions
NTRK3	LYN-NTRK3.L8N14	Fusion	3	NTRK3 Gene Fusions

NTRK3	RBPMS-NTRK3.R5N14	Fusion	3	NTRK3 Gene Fusions
-------	-------------------	--------	---	--------------------

## APPENDIX X: CTEP AND CTSU REGISTRATION PROCEDURES

Food and Drug Administration (FDA) regulations and National Cancer Institute (NCI) policy require all individuals contributing to NCI-sponsored trials to register and to renew their registration annually. To register, all individuals must obtain a Cancer Therapy Evaluation Program (CTEP) Identity and Access Management (IAM) account at <https://ctepcore.nci.nih.gov/iam>. In addition, persons with a registration type of Investigator (IVR), Non-Physician Investigator (NPIVR), or Associate Plus (AP) must complete their annual registration using CTEP's web-based Registration and Credential Repository (RCR) at <https://ctepcore.nci.nih.gov/rcr>.

RCR utilizes five person registration types.

- IVR — MD, DO, or international equivalent;
- NPIVR — advanced practice providers (e.g., NP or PA) or graduate level researchers (e.g., PhD);
- AP — clinical site staff (e.g., RN or CRA) with data entry access to CTSU applications such as the Roster Update Management System (RUMS), OPEN, Rave, acting as a primary site contact, or with consenting privileges;
- Associate (A) — other clinical site staff involved in the conduct of NCI-sponsored trials; and
- Associate Basic (AB) — individuals (e.g., pharmaceutical company employees) with limited access to NCI-supported systems.

RCR requires the following registration documents:

Documentation Required	IVR	NPIVR	AP	A	AB
FDA Form 1572	✓	✓			
Financial Disclosure Form	✓	✓	✓		
NCI Biosketch (education, training, employment, license, and certification)	✓	✓	✓		
GCP training	✓	✓	✓		
Agent Shipment Form (if applicable)	✓				
CV (optional)	✓	✓	✓		

An active CTEP-IAM user account and appropriate RCR registration is required to access all CTEP and Cancer Trials Support Unit (CTSU) websites and applications. In addition, IVRs and NPIVRs must list all clinical practice sites and Institutional Review Boards (IRBs) covering their practice sites on the FDA Form 1572 in RCR to allow the following:

- Addition to a site roster;
- Assign the treating, credit, consenting, or drug shipment (IVR only) tasks in OPEN;
- Act as the site-protocol Principal Investigator (PI) on the IRB approval; and
- Assign the Clinical Investigator (CI) role on the Delegation of Tasks Log (DTL).

In addition, all investigators acting as the Site-Protocol PI (investigator listed on the IRB approval), consenting/treating/drug shipment investigator in OPEN, or as the CI on the DTL must be rostered at the enrolling site with a participating organization.

Additional information is located on the CTEP website at <https://ctep.cancer.gov/investigatorResources/default.htm>. For questions, please contact the RCR **Help Desk** by email at [[contact]](mailto:[contact]).

